Demographic data and data from assessments at baseline were collected on the same day for each of the participants. Follow-up data from all baseline assessments, additionally Patient Global Impression of Change (PGIC), were collected 4-5 months after enrolment.

Follow-up data limited to self-reported questionnaires were collected 12-13 months after enrolment. Questionnaires were distributed per e-mail using the web-based program InfoPad, and all questionnaires are to be filled out in one single session.

Primary Outcomes

- 1) Numeric Rating Scale (NRS) for pain during walking is a primary outcome, scale 0-10. A change ≥ 15.3 mm on a 0-100 scale is considered clinically important in hip OA^{26,27}.
- 2) Hip Osteoarthritis Outcome Score (HOOS) is an instrument to assess the patients' opinion about their hip and associated problems, as perceived during the last week

before measurement ²⁸. It contains questions of five domains; pain (P) - 10 items, symptoms (S), - 5 items, Activities of Daily Life (A), - 17 items, sport and recreation (SP) - 4 items, and hip related quality of life (QL) - 4 items ²⁹. Each item is answered on a Likert scale (no, mild, moderate, severe, extreme) and scored from 0-4. The sum score of each domain is transformed to a normalized 0-100 scale, where 0 indicates extreme problems and 100 no problems. HOOS has shown high test-retest reliability (ICC for subscales ranging from 0.78 to 0.91) ²⁸. Construct validity has been supported by high correlations with the Oxford Hip Score ($r_s = 0.822$) and the SF-36 ($r_s = -0.664$)³⁰. The HOOS ADL subscale is a primary outcome.

Secondary outcomes:

1) Chairs test

The chairs test is a quantitative test of a functional activity. The patient repeats rising up from a chair and sitting down during 30 seconds, and the number is counted. Intra-rater and inter-rater reliability is high in patients with hip or knee OA, with $ICC = 0.85$ and 0.86 , respectively ³¹. A minimal clinical important improvement of $2.0 - 2.6$ stands have been reported (Wright, 2011)

2) Stairs test

The stairs test is a quantitative test of a functional activity. The time by number of seconds used to walk up and down 18 steps x 3 is measured³².

3) 6-minutes walking – test (6MWT)

Walking as far as possible during the course of 6 minutes without running. Distance is measured in meter. Minimal detectable change is 61.34 meters³².

4) University of California Los Angeles activity score (UCLA)

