^{26,27}, we assumed a between-participant standard deviation of change of 30 points. The required sample size, with 80% power and the significance level of 0.05 was 44 in each group. Allowing for a 15% drop-out, a total of 100 patients was required. Disability was assessed by the Hip disability and Osteoarthritis Outcome Score (HOOS). Referring to power calculation of a previous relevant study, 74 patients are needed to detect a clinically relevant change of 10 points on the subscale in patients with hip pain ($SD \pm 15$, power = 0.80 and $\alpha = 0.05$)¹⁵. A total of 100 patients were, accordingly, a sufficient sample size for both measures.

The intervention, BBAT, has been tried out in a pilot study showing promising results and has shown positive results in other patient groups⁴⁴. No adverse effects have been reported. Plans for interim analyses or stopping guidance were therefore not considered relevant.

Adherence and protocol deviations

Definition of adherence to the intervention and how this is assessed including extent of exposure

The physiotherapist leading the BBAT group kept a record over patient attendance. Patients that participate at least 10 times in BBAT groups are regarded to having completed the intervention. A table will show the number of BBAT group sessions attended to during the intervention period.

Definition of protocol deviations for the trial

No deviations from the original protocol.

Definition of analysis populations

All participants (n = 101) will be included in an intention to treat (ITT) analysis investigating the effectiveness of BBAT groups in clinical and practical settings; a real life situation. Patients who have completed the treatment (10 BBAT group sessions) and have been available for all baseline and 4-5 month follow-up measurements, are included in a per protocol analysis (PPA) investigating the maximum treatment efficacy in perfect compliers.

Withdrawal/follow-up

A flow-chart will be made to show the level of patient participation throughout the study, illustrating withdrawals/lost to follow-up data in both groups separately, with timing and reasons for withdrawal/lost to follow-up.

Statistical analysis plan

The present statistical analysis plan will be made publicly through registration in ClinicalTrials before any analysis is performed. The statistical analyses will be performed in close collaboration with an independent statistician who is unaware of group assignment.

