The general significance level is set to 0.05. Using Bonferroni adjustment for 2 tests (2 primary outcomes; NRS and HOOS A), 0.025 is set as a marginal level. Residual plots will be used to check for normality assumptions and homoscedasticity. A per protocol analysis (PPA) will be used for sensitivity analysis for all outcomes. Subgroups related to cartilage thickness (0 versus > 0) will be investigated using a stratified ANCOVA as described above, if sufficient number of observations is available in both groups.

Missing data

Missing data will be investigated for any relations to the intervention or outcomes of interest (missing at random). Assuming the data missing at random, multiple imputation methods (MIM) will be used to generate random estimates, if necessary.

Missing items in patient reported questionnaires will be handled in accordance with guidelines for the questionnaire. If no guideline is available, mean imputation will be used if less than 10% of the items are missing.

Additional analyses

ANCOVA adjusted for concomitant treatments reported by participants will be conducted.

Harms

No adverse effects or risks of harm are documented from studies on PE or BBAT groups. If adverse events should occur, they will be categorized as treatment related or not, and treatment related events will be summarized and compared between groups.

Statistical software

IBM SPSS 24⁴⁶ and R⁴⁷ will be used for data handling and analyses.

References

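### Read literally, the per-protocol set drops patients from every outcome for one unrelated test not done, which is selection that has nothing to do with adherence

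*SAP*

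**What the plan says.** Under Definition of analysis populations, the SAP admits to the per-protocol analysis those who completed the treatment, set there at 10 BBAT group sessions, and who "have been available for all baseline and 4-5 month follow-up measurements". It gives the purpose as "investigating the maximum treatment efficacy in perfect compliers". Completion is defined under Adherence and protocol deviations: "Patients that participate at least 10 times in BBAT groups are regarded to having completed the intervention".

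The section Statistical analysis plan sets the scope: "A per protocol analysis (PPA) will be used for sensitivity analysis for all outcomes". No other analysis in the SAP is labelled a sensitivity analysis, and no per-protocol set specific to an outcome is defined.

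On what the measurements are, Data collection and outcomes states: "Follow-up data from all baseline assessments, additionally Patient Global Impression of Change (PGIC), were collected 4-5 months after enrolment". They include physical tests such as the stairs test: "The time by number of seconds used to walk up and down 18 steps x 3 is measured".

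By contrast, "All participants (n = 101) will be included in an intention to treat (ITT) analysis", with multiple imputation if needed (Missing data).

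**The concern.** The set has two entry conditions. The first, attendance, matches the stated aim of studying compliers. The second concerns measurement. As worded it covers all instruments at both visits, whichever outcome is being analysed.

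A patient with 12 sessions and NRS and HOOS ADL recorded at both visits would therefore leave both primary-outcome per-protocol analyses if the 6-minute walk was not done at one visit. Nothing about that patient's adherence or primary-outcome data justifies this. Inability or unwillingness to do a walking or stair test may also be related to hip pain and function. That is plausible rather than shown in the SAP, but if so, the exclusion is not random with respect to the outcomes.

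At stake is the meaning and the size of the SAP's only named sensitivity analysis. The primary result is not at stake.

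**Working it through.** **Is there a figure to reproduce?** No. The SAP gives neither an expected size for the per-protocol set nor a missing rate per measurement. Its only attrition figure is the 15% drop-out allowance under Sample size, which concerns loss of patients, not skipped tests. The missing rates below are assumptions, shown as a range.

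**Counting the occasions** (from Primary Outcomes, Secondary outcomes, and the statement that PGIC is added at follow-up):

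- Baseline instruments: NRS, HOOS, chairs, stairs, 6MWT, UCLA, ASES, EQ-5D-5L, HHS, BARS-MQE = 10.
- At 4-5 months: the same 10 plus PGIC = 11.
- Total instrument-occasions: 10 + 11 = 21.
- NRS and HOOS at two visits carry the primary outcomes, so they are not unrelated measurements: 21 − 4 = 17 remain.
- Physical tests only (chairs, stairs, 6MWT, BARS-MQE) at two visits: 4 × 2 = 8.

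**Formula.** If each occasion is missing independently with probability q, the share of patients with at least one of k occasions missing is 1 − (1 − q)^k.

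| q | k = 8 (physical tests) | k = 17 (all except NRS and HOOS) | k = 2 (own baseline and follow-up value) |
|---|---|---|---|
| 0.5% | 1 − 0.995^8 = 3.9% | 1 − 0.995^17 = 8.2% | 1 − 0.995^2 = 1.0% |
| 1% | 1 − 0.99^8 = 7.7% | 1 − 0.99^17 = 15.7% | 1 − 0.99^2 = 2.0% |
| 2% | 1 − 0.98^8 = 14.9% | 1 − 0.98^17 = 29.1% | 1 − 0.98^2 = 4.0% |

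The columns for k = 8 and k = 17 are the additional loss among patients who meet the attendance criterion and have the outcome's own values. The last column is the loss that any rule needing the outcome's own two values would incur.

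**What moves these figures.** Independence gives the larger loss. The SAP says that baseline data were collected on one day and that questionnaires are filled out in a single session, so missing values should cluster by visit. A patient who misses the whole 4-5 month visit also lacks NRS and HOOS and would be excluded under either rule. Single missing questionnaire items are handled under Missing data and need not trigger exclusion. That provision does not help with a physical test that was not done, so the 8-occasion column is closest to the mechanism described here.

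**The case against.** The strongest reply is that being available for the measurements may simply mean attending both assessment visits. That is a natural reading, and under it a skipped stairs test excludes nobody. It stands as a real alternative, but the SAP does not say which meaning applies. The per-protocol analysis is scheduled after the randomisation code is broken, so whoever settles the meaning at that point could know the allocation. It is better settled in the text.

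A second reply is that one common set keeps the same patients in every table and suits the aim of studying perfect compliers. The consistency is a genuine convenience. However, complying with BBAT and completing every test are different things, and the stated aim concerns the former.

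Third, the stakes are limited. This is correct: the intention-to-treat analysis keeps all 101 participants, and no primary conclusion rests on the per-protocol set.

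Three stronger readings are tempting and are not supported:

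- A reader might infer that all 21 occasions count as unrelated to the primary outcomes. Four of them are the NRS and HOOS assessments themselves.
- A reader might infer that the rule is wrong for 12-13 month outcomes. The SAP schedules a per-protocol analysis only for the short-term data, and its reference to all outcomes does not say all time points.
- A reader might infer that the selection acts in both arms. The sentence joins availability to the BBAT sessions and does not say how comparison patients enter the set, so nothing can be concluded about selection by arm.

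**Conclusion.** The point holds on the literal wording. One availability condition over all measurements governs a single set used for every outcome, so patients with usable primary-outcome data can be excluded because of an unrelated test. This adds selection unrelated to adherence and needlessly reduces the n of a secondary sensitivity analysis.

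The size cannot be established from the SAP. Under the assumed independent missing rates of 0.5% to 2%, it runs from about 4% to 15% for the physical tests alone and from about 8% to 29% for all 17 other occasions. It is lower with clustering by visit, and small if availability means attendance at both visits.

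A reader might also infer that, without this condition, a difference between the intention-to-treat and per-protocol results would show the effect of attendance. It would not: reaching 10 sessions is itself a selection made after randomisation. Changing the rule removes one avoidable source of difference, not all of them.

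**What to change.** Under Definition of analysis populations, replace the all-measurements condition with the attendance criterion plus the baseline value and the analysed follow-up value of the outcome concerned. Show the per-protocol n in each table. If the per-protocol analysis is also intended for 12-13 months, state this and make the 12-13 month value the one required there.

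The cost is about one sentence in the SAP. The drawback is that the per-protocol n will differ between outcomes, so the tables no longer describe one identical group of patients. When reporting, note that any difference from the intention-to-treat result still reflects selection on attendance.

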HHS is used to assess hip disabilities and effect of treatment on four domains. Grading of scores: <70=poor, 70-79=fair, 80-89= Good, 90-100 Excellent. A successful result: >20 points⁴⁰.
- 10) **Body Awareness Rating Scale—Movement Quality and Experience (BARS-MQE)**
BARS-MQE consists of two intertwining parts. In Part 1, the physiotherapist observes, evaluates and scores the patient's MQ in 12 daily-life movements and actions: lying, sitting, standing, walking and moving in relation to another person⁴¹. Each movement is followed by Part 2, an open-ended question on the patient's immediate experiences from exploring the movement²⁰. Part 2 is not included in the present study. The observed MQ in each of the 12 movements is scored on an ordinal scale from 1 (dysfunctional MQ, described as unstable, mechanical, stiff and with a lack of unity), to 7 (functional MQ, described as balanced, free, centered, unified, rhythmic and synchronous)²³. The sum score of the 12 movements ranges from 12 to 84. In a study of patients with long-lasting musculoskeletal disorders and mental health problems, reliability of the BARS-MQE was found highly satisfactory. Internal consistency by Cronbach's alpha was 0.92, and ICCs of inter-tester and test-retest reliability 0.99 and 0.96, respectively. BARS-MQE was found to correlate moderately with most subscales of the Short-Form Health Survey (SF-36) and with the General Perceived Self-Efficacy Scale (GPSES), and to discriminate between patients and healthy persons⁴².

Statistical methods

Sample size

The necessary sample size was estimated based on the two primary outcomes; hip pain and function in daily life activities. Pain was assessed by the 0-100 Numeric Rating Scale (NRS). The expected difference in change between the groups was 18 points on the NRS, which is considered the minimum important difference in improvement⁴³. Based on previous studies

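### Single-step Bonferroni at 0.025 for each primary outcome is valid but needlessly conservative; Holm within each follow-up keeps the same 5% error for the pair and gains some power if both effects are real

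*SAP*

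**What the plan says.** The section "Statistical analysis plan" of the SAP states "The general significance level is set to 0.05" and then "Using Bonferroni adjustment for 2 tests (2 primary outcomes; NRS and HOOS A), 0.025 is set as a marginal level". It gives no step-down rule and no way to pass alpha on once one outcome is significant. The same section plans separate ANCOVAs at the two follow-ups (4-5 and 12-13 months), plus a linear mixed model.

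The Sample size section treats both outcomes as the basis of the trial: "The necessary sample size was estimated based on the two primary outcomes; hip pain and function in daily life activities". For pain, "The expected difference in change between the groups was 18 points on the NRS" and "we assumed a between-participant standard deviation of change of 30 points", which leads to "The required sample size, with 80% power and the significance level of 0.05 was 44 in each group". For HOOS ADL, "74 patients are needed to detect a clinically relevant change of 10 points on the subscale in patients with hip pain", with a standard deviation of 15 and 80% power at 0.05. Enrolment closed at 101.

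**The concern.** With single-step Bonferroni the second outcome gains nothing when the first succeeds. Suppose NRS pain gives p = 0.003 and HOOS ADL p = 0.04. Under the stated rule HOOS ADL misses its 0.025 threshold. Under Holm it passes, because the smaller p-value has cleared 0.025 and the larger is then compared with 0.05. The 5% family-wise error for the pair is kept either way.

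Power is at stake in a trial whose size can no longer change. The sample size was worked out at 0.05 per outcome while testing is at 0.025, so the fixed threshold already costs power against the planned 80%. Holm recovers part of that without further patients.

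**Working it through.** **Inputs from the SAP.** Pain: difference 18, SD 30, so d = 18/30 = 0.60. HOOS ADL: difference 10, SD 15, so d = 10/15 = 0.667. Loss 15%; enrolled 101. Evaluable per arm: 101 × 0.85 / 2 = 42.9, taken as 43.

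**Assumptions, not in the SAP.** Two-sided tests (these reproduce the stated sample size); correlation ρ between the two outcomes, varied from 0 to 0.8; for ANCOVA, correlation r between baseline and follow-up, varied from 0.3 to 0.7, with equal variances at the two times.

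**1. The plan's own figures.** n per arm = 2(z₀.₉₇₅ + z₀.₈₀)² / d².
- Pain: 2 × (1.960 + 0.842)² / 0.36 = 43.6, so 44. This matches the SAP.
- HOOS ADL: 2 × (1.960 + 0.842)² / 0.444 = 35.3, so 36 per arm or 72 in total. The stated 74 (37 per arm) gives t-test power of 0.81, which is consistent.

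**2. Cost of the fixed 0.025.** Power of the two-sample t-test, df = 2n − 2, noncentrality d√(n/2), at 43 per arm:
- Pain: 78.5% at 0.05, 69.1% at 0.025.
- HOOS ADL: 86.3% at 0.05, 78.9% at 0.025.

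**3. Holm against Bonferroni, both planned effects real.** Holm rejects an outcome if its p ≤ 0.025, or if its p ≤ 0.05 and the other outcome's p ≤ 0.025. Simulated pairs of t statistics, 43 per arm (power in %):

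| ρ | Pain, Bonferroni → Holm | HOOS ADL, Bonferroni → Holm | At least one, either rule |
|---|---|---|---|
| 0 | 69.2 → 76.6 | 79.0 → 84.1 | 93.5 |
| 0.3 | 69.1 → 76.1 | 78.9 → 83.3 | 90.3 |
| 0.5 | 69.1 → 75.9 | 78.9 → 82.8 | 87.9 |
| 0.7 | 69.2 → 75.7 | 78.9 → 82.1 | 85.2 |
| 0.8 | 69.1 → 75.6 | 78.9 → 81.5 | 83.5 |

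The gain is 6.5 to 7.4 points for pain and 2.6 to 5.1 for HOOS ADL.

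**4. Under the planned ANCOVA.** With equal variances the residual SD is √((1 + r)/2) times the SD of change. The factor is 0.806, 0.866 and 0.922 for r = 0.3, 0.5 and 0.7. With 43 per arm and ρ = 0.5:

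| r | Pain, Bonferroni → Holm | HOOS ADL, Bonferroni → Holm |
|---|---|---|
| 0.3 | 87.6 → 91.9 | 93.8 → 95.7 |
| 0.5 | 82.1 → 87.5 | 89.8 → 92.5 |
| 0.7 | 76.7 → 82.8 | 85.6 → 88.8 |

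The gain is 4.3 to 6.1 points for pain and 1.9 to 3.2 for HOOS ADL.

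**5. Only one effect real** (43 per arm, t-test, ρ = 0). Pain only: 69.1 → 69.3%. HOOS ADL only: 78.9 → 79.1%. The gain is about 0.2 points, and smaller still at higher ρ.

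**6. Error control.** With no effect on either outcome, the chance of any false rejection is the same under both rules: 5.0%, 4.7% and 4.1% at ρ = 0, 0.5 and 0.8. With one true effect, Holm falsely rejects the other outcome in at most 4.5% of trials.

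**The case against.** The strongest reply is that nothing here is wrong. Bonferroni at 0.025 is prespecified, simple, and controls the error it claims to control for the two named outcomes. That stands, and it is why this is an improvement and not a correction.

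The size of the loss is also open to challenge. The 69% and 79% come from a t-test on change, whereas the SAP plans ANCOVA and allows multiple imputation. If baseline and follow-up correlate at 0.3 to 0.5, Bonferroni already exceeds 80% power for both outcomes and Holm adds less. This stands too, so both sets of figures are given. It also stands that the gain almost vanishes if only one effect is real; at half the planned effects (43 per arm, ρ = 0.5) it is about 3 points for pain and 2.5 for HOOS ADL.

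Three stronger readings are tempting, and the SAP does not support them.
- A reader might infer that HOOS ADL at p = 0.04 would be reported as no effect on function. The SAP sets a threshold but does not say this, and it also plans a responder analysis and a discussion of clinically meaningful change for both outcomes.
- A reader might treat significance on both outcomes as the success criterion and quote that power (60.1 → 70.7% at ρ = 0.5 with the t-test). The SAP nowhere requires both.
- A reader might call the change free. It costs no alpha and no patients, but the simple 97.5% simultaneous intervals that go with Bonferroni no longer match the decision.

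The objection does not touch the main argument: at equal error control for the pair, the chosen rule can only reject the same or less.

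**Conclusion.** The point holds as a modest gain in efficiency. Its size is the 6-7 and 3-5 points in step 3, or the 4-6 and 2-3 points of the ANCOVA range, for pain and HOOS ADL respectively. These figures rest on both planned effects being real and on correlations that the SAP does not give.

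The 5% statement applies to the pair at one follow-up. A reader might infer that Holm gives 5% control for the whole set of primary tests. It does not: the SAP tests both outcomes at two follow-ups separately and adjusts for two tests only, and Holm on two tests leaves that as it is. Nor does Holm fully close the gap between sizing at 0.05 and testing at 0.025: with the change-score SDs and 43 per arm, pain stays below 80%.

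**What to change.** In the section "Statistical analysis plan", replace the Bonferroni sentence by: *At each follow-up time point, the two primary outcomes are tested with the Holm procedure at 0.05 for the pair: the smaller p-value is compared with 0.025 and, only if significant, the larger with 0.05.* Report Holm-adjusted p-values beside the estimates. Naming the time point matters, because two outcomes at two follow-ups give four p-values and the pair must be defined.

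The cost is one sentence, made before any analysis, with no further patients or data. If unadjusted 95% intervals are shown, state that they are not simultaneous and need not agree with the Holm decision. Multiplicity across the two follow-ups needs its own decision.

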Disease processes and pain in osteoarthritis are known to have an impact on the patients' movement pattern, leading to dysfunctional habits with additional strain on the joint and other body parts¹⁷. Although physiotherapists observe and attend to the quality of patients' movement performance during exercise, correcting guidance is mainly focused on maintaining physiological joint angles or activating specified muscles¹⁸. From qualitative studies, it is well-known that patients with hip osteoarthritis, similar to other long-lasting pain conditions, experience changes in the way they perceive their body in movement and at rest^{19,20}. Their sensitivity to nuanced body perceptions may be disturbed and reduced by sensations of pain. Patients' way of coping with the disease is also influenced by how they interpret and act on bodily perceptions. For example is it likely that flares of increased pain is understood by patients as a sign for increased disease severity, and that they consequently develop negative beliefs and/or feelings of helplessness. The present study will investigate effects from Basic Body Awareness Therapy (BBAT), a movement learning program that aims to address patients movement habits based on enhanced movement awareness²¹. Revealing and utilizing own resources for movement under physiotherapy guidance is regarded to help patients understand and handle bodily signals in such a way that they develop functional movement patterns as well

as constructive ways of dealing with their disease. Hence, BBAT aims to address health aspects described in the bio-psycho-social model, based on the patients' active involvement, their movement experiences and their movement learning process^{22,23}.

Objectives and hypotheses

The purpose of this study is to examine the supplementary short- and long-term effects of BBAT in patients with hip OA, by comparing the outcomes (pain, functioning, and quality of life) of Patient Education (PE) alone with PE and BBAT combined. It is hypothesized that patients that participate in BBAT group therapy following PE show more short-term (4-5 months) and long-term (12-13 months) improvements compared to patients that participate in PE only.

Design and methods

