Intention-to-treat analysis of short-term follow-up data (4-5) months is performed during the fall 2019. To reduce the risk of bias during interpretation, blinded study results will be presented

to all authors. A researcher not involved with the study is asked to add A and B to the data sheet in line with the list of randomized participants, but without breaking the randomization code. Per protocol analysis of short-term data will be carried out after breaking the randomization code (spring 2020).

The long-term and final analyses of primary and secondary outcomes, as well as subgroup analyses related to cartilage thickness and additional treatment, will be conducted after data collection at 12-month follow-up is completed, the database is closed and the randomization code is broken (spring 2020).

Demographic data and characteristics of participants (e.g. age, height, weight, cartilage thickness, comorbidities, work status, type of work and medications) will be presented using descriptive statistics. Normality of continuous variables will be inspected visually on Q-Q plots. Mean and standard deviation will be used to describe normally distributed continuous variables, and median and upper and lower limits of the interquartile range to describe non-normally distributed continuous variables. Counts and percentages will be used to present categorical variables. No statistical testing will be performed to investigate differences in baseline characteristics between groups.

Differences between groups at both follow-up time points will be investigated separately using analysis of covariance (ANCOVA). Additionally, we will estimate a linear mixed effects model, including all time points, effect of treatment and their interaction.

In line with a patient-centred perspective, the clinical meaningful interpretation of change scores on the two primary outcomes, NRS Pain during walking and HOOS subscale ADL, will be discussed. A responder analysis will be conducted, based on values of minimal clinically important improvement (MCII) as anchors. No studies have, so far, calculated a MCII value for NRS Pain during walking or HOOS ADL in relation to physiotherapy. The values will therefore be defined as the mean change in scores in the category of patients who report to be “slightly improved” in pain and function on the PGIC⁴⁵. The proportions of responders in the intervention- versus control group will be analysed.

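### The cartilage-thickness subgroup analysis estimates effects within strata but plans no treatment-by-cartilage interaction or other comparison of them

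*SAP*

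**What the plan says.** The subgroup method is given in one sentence of the SAP's statistical analysis plan section: "Subgroups related to cartilage thickness (0 versus > 0) will be investigated using a stratified ANCOVA as described above", subject to the condition "if sufficient number of observations is available in both groups". What counts as sufficient is not defined.

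The analysis referred to is the main one: "Differences between groups at both follow-up time points will be investigated separately using analysis of covariance (ANCOVA". No cartilage term is mentioned there. The next sentence adds that "we will estimate a linear mixed effects model, including all time points, effect of treatment and their interaction", which is an interaction of treatment with time.

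Cartilage thickness appears in two other places in the same section. It is listed among the descriptive participant characteristics, and it comes up in the timing of the analyses: "subgroup analyses related to cartilage thickness and additional treatment, will be conducted after data collection at 12-month follow-up is completed". Under Additional analyses, "ANCOVA adjusted for concomitant treatments reported by participants will be conducted" concerns covariate adjustment and adds no subgroup contrast.

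**The concern.** A subgroup analysis by cartilage thickness is useful mainly for asking whether the treatment effect depends on cartilage. Two stratum effects reported side by side do not answer that. The answer is the difference between them, with its own standard error, and the SAP does not plan to estimate it.

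The danger is a familiar misreading: one stratum reaches significance, the other does not, and the treatment is said to work in one type of patient only. In small strata this happens often when the true effects are equal. The subgroup analyses are scheduled for after the randomisation code is broken, so a contrast added at that stage would be post hoc.

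**Working it through.** **1. What the text specifies.** "Stratified" can be read in two ways.
- Separate ANCOVAs in each stratum give two treatment effects that are never compared.
- One ANCOVA with cartilage as a stratification factor gives a single adjusted effect, and again no comparison.

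The gap exists on both readings. The figures in steps 3 to 5 apply to the first.

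**2. The SAP's own sample size.** The inputs, from the Sample size section, are a difference of 18 points on the NRS, SD of change 30, 80% power and a significance level of 0.05, taken as two-sided. Then n per arm = 2 × (30/18)² × (1.960 + 0.842)² = 43.6, rounded up to 44. This matches the stated 44 per group.

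**3. How often exactly one stratum is significant when the true effects are equal.** Assumptions:
- 44 analysed per arm and equal allocation within strata.
- Splits of about 50/50, 30/70 and 20/80, since the SAP gives none. Per arm these are 22/22, 13/31 and 9/35.
- Two-sample t tests with the SAP's SD, ignoring any precision gained from baseline adjustment.

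With stratum powers p1 and p2 (noncentral t), P(exactly one) = p1(1 − p2) + p2(1 − p1). For NRS pain, 18 points, alpha 0.05:

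| Per arm in strata | p1 | p2 | P(exactly one) |
|---|---|---|---|
| 22 / 22 | 0.494 | 0.494 | 0.500 |
| 13 / 31 | 0.312 | 0.642 | 0.553 |
| 9 / 35 | 0.224 | 0.697 | 0.609 |

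For example, in the third row: 0.224 × 0.303 + 0.697 × 0.776 = 0.609.

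P(exactly one) across the three splits, including other effects and the 0.025 level that the SAP sets for its two primary outcomes:

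| Outcome and true effect | alpha 0.05 | alpha 0.025 |
|---|---|---|
| NRS, 18 points | 50–61% | 47–56% |
| NRS, 9 points | 27–28% | 18–19% |
| No effect | 9.5% | 4.9% |
| HOOS ADL, 10 points (SD 15) | 49–63% | 50–62% |
| HOOS ADL, 5 points (SD 15) | 31–33% | 21–23% |

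Using all 101 participants (with a normal approximation) gives 49% to 62% for NRS at 18 points and alpha 0.05, so the choice of 44 per arm hardly matters.

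**4. What an interaction test would do in the same trials.** In simulation (200,000 trials per case, equal effects) it rejects in 4.9% to 5.1% of trials. Among trials with exactly one significant stratum at the 18-point effect, it is significant in 9.6%, 8.0% and 6.7% for the three splits.

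**5. How informative the interaction is.** SE = SD × √(2/n1 + 2/n2), with 88 − 5 = 83 degrees of freedom. For NRS at 22/22: 30 × √(2/22 + 2/22) = 12.8.

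| Per arm in strata | NRS SE | 95% CI half-width | Power for 18 points | HOOS SE | 95% CI half-width | Power for 10 points |
|---|---|---|---|---|---|---|
| 22 / 22 | 12.8 | 25.4 | 0.285 | 6.4 | 12.7 | 0.339 |
| 13 / 31 | 14.0 | 27.9 | 0.245 | 7.0 | 13.9 | 0.292 |
| 9 / 35 | 15.9 | 31.5 | 0.202 | 7.9 | 15.8 | 0.239 |

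**The case against.** The SAP makes no claim that needs an interaction. Its hypothesis is about the overall effect, that "patients that participate in BBAT group therapy following PE show more short-term (4-5 months) and long-term (12-13 months) improvements" compared with education only. It sets no decision rule for subgroups, and stratum-specific estimates are a legitimate descriptive aim. The difference between them could be calculated afterwards. The sufficient-numbers condition might exclude the very uneven splits that give the highest percentages. The percentages also rest on one reading of "stratified" and ignore the precision gained by baseline adjustment. At the larger effects, discordant strata mostly reflect low power within strata, which an interaction term does not cure, and the interaction would usually be inconclusive.

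Much of this stands, and it limits the severity: the harm is conditional and the percentages are illustrative. It does not remove the point. The SAP itself chose the variable, the cut-point and the method, and on either reading that method cannot show whether the effect differs by cartilage. The sufficient-numbers condition has no threshold, so it cannot be relied on to exclude any split, and even the 50/50 split gives 50%. The low power of the interaction is a reason to report it: a half-width of 25 to 32 NRS points shows openly how little the data can say, which two separate p-values do not.

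**Conclusion.** The concern holds, as a minor one. The SAP plans a cartilage subgroup analysis without any treatment-by-cartilage interaction or other contrast of the stratum effects. The primary comparison is not affected.

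The size of the problem depends on a reading that the SAP does not state. If significance in one stratum only were taken as evidence of a difference, it would mislead in roughly half or more of trials at the 18-point design effect, in about 27% to 28% at half that effect, and in 9.5% with no effect (alpha 0.05). The absence of a contrast follows from the text and depends on none of the numerical assumptions.

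**What to change.** Replace the stratified ANCOVA with a single model at each follow-up containing group, baseline score, cartilage (0 versus > 0) and group-by-cartilage. Report the interaction estimate with its 95% CI and take the two stratum effects from the same model. State that any claim of a differential effect rests on the interaction, and label the analysis exploratory.

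The cost is one sentence in the SAP and one product term. Cartilage thickness is already among the listed participant characteristics, so no new data or patients are needed. The drawback is imprecision: power is about 20% to 29% for an 18-point NRS difference between strata and 24% to 34% for 10 points on HOOS ADL. The SAP should therefore also say that a non-significant interaction does not show equal benefit.
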